### 6.13.3.12.1. Acute Renal Events

Because severe GI events may lead to dehydration, which could cause a deterioration in renal function including acute renal failure, dehydration events will be analyzed. Acute renal events associated with chronic renal failure exacerbation will also be captured.

Acute renal events from the following SMQ search will be considered as AESIs.

The counts and percentages of participants with acute renal events will be summarized by treatment by using the MedDRA PTs contained in any of the following SMQs:

- Acute renal failure: Narrow terms in Acute renal failure SMQ (2000003) and
- Chronic kidney disease: Narrow terms in Chronic kidney disease SMQ (2000213).

In addition, a listing of participants with treatment-emergent acute renal events may be provided, if deemed necessary.

### 6.13.3.12.2. Dehydration

Dehydration events will be captured in the Narrow terms in Dehydration SMQ (20000232). Severe/serious dehydration events will be considered AESIs.

A listing of participants with treatment-emergent dehydration events will be provided.

### 6.13.3.13. Thyroid Safety Monitoring

### 6.13.3.13.1. Calcitonin

Observed calcitonin data (a thyroid-specific laboratory assessment) will be summarized by treatment and nominal visit.

The counts and percentages of participants with a maximum postbaseline calcitonin value in the following thresholds will be provided by treatment and baseline calcitonin value ( $\leq 20 \text{ ng/L}$ ,  $\geq 20 \text{ ng/L}$  to  $\leq 35 \text{ ng/L}$ ,  $\geq 35 \text{ ng/L}$ ). Postbaseline:  $\leq 20 \text{ ng/L}$ ,  $\geq 20 \text{ ng/L}$  to  $\leq 35 \text{ ng/L}$ ,  $\geq 30 \text{ ng/L}$ ,  $\geq 20 \text{ ng/L$ 

### 6.13.3.13.2. C-Cell Hyperplasia and Thyroid Malignancies

Treatment-emergent thyroid malignancies and C-Cell hyperplasia will be considered AESIs. Detailed searching criteria can be found in Appendix 1.

The counts and percentages of participants with treatment-emergent thyroid C-cell hyperplasia and malignancies will be summarized by treatment and PT ordered with decreasing frequency. In addition, a listing of participants with treatment-emergent thyroid C-cell hyperplasia and neoplasms may be provided if deemed necessary.

### 6.13.3.14. Treatment-Emergent Arrhythmias and Cardiac Conduction Disorders

Treatment-emergent arrhythmias and cardiac conduction disorders will be considered as AESIs.

The treatment-emergent arrhythmias and cardiac conduction disorders events will be included using the MedDRA PTs. Detailed searching criteria can be found in Appendix 1.

The counts and percentages of participants with treatment emergent arrhythmias and cardiac conduction disorders will be summarized by treatment and PT nested within SMQ. The PT will be ordered with decreasing frequency within SMQ. A listing of participants with treatment-emergent arrhythmias and cardiac conduction disorders may be provided if deemed necessary.

### 6.13.3.15. Overdose

A listing of patients reporting AEs related to overdosing of tirzepatide will be provided.

### 6.13.3.16. Abuse Liability

The counts and percentages of participants with treatment emergent potential abuse liability events will be summarized by treatment group with decreasing frequency. Detailed searching criteria can be found in Appendix 1.

### 6.13.4. Vital Signs

In the case that multiple records of an individual vital sign are collected at the same visit, they will be averaged prior to being used for data summaries and analyses.

Descriptive summaries by treatment and by nominal visit will be provided for baseline and postbaseline values as well as change from baseline values.

An MMRM and/or an ANCOVA model as in Section 6.13 might be conducted if necessary.

Counts and percentages of participants with treatment-emergent abnormal sitting SBP, sitting DBP, and pulse will be presented by treatment for participants who have both baseline and at least 1 postbaseline result. A treatment-emergent high result is defined as a change from a value less than or equal to the high limit at baseline to a value greater than the high limit at any time that meets the specified change criteria during the postbaseline period. A treatment-emergent low result is defined as a change from a value greater than or equal to the low limit at baseline to a value greater than be low limit at baseline to a value less than the low limit at any time that meets the specified change criteria during the postbaseline period. To assess decreases, change from the minimum value during the baseline period to the minimum value during the postbaseline period will be used. To assess increases, changes from the

## 6.13.5. Electrocardiograms

For electrocardiogram (ECG) parameters that collect in triplicates (ie, Visit 3 and Visit 12), the average from the 3 measurements for the same parameter at the same visit will be calculated and used for all the subsequent summaries and analyses.

Summary statistics by treatment and by nominal visit will be provided for ECG parameters (heart rate, PR, QRS, QT, and QT corrected using Fredericia's correction factor  $[QTcF = QT / RR^{0.333}]$ ). When the QRS is prolonged (eg, a complete bundle branch block), QT and QTc should be used to assess ventricular repolarization. Thus, for a particular ECG, the following will be set to missing (for analysis purposes) when QRS is  $\geq 120$  msec: QT and QTcF.

Change from baseline to postbaseline values for ECG parameters will be summarized for patients who have both a baseline and at least 1 postbaseline result. Only planned measurements will be included in the mean change analyses.

The criteria for identifying participants with treatment-emergent quantitative ECG abnormalities is based on Table GPIA.6.10.

The counts and percentages of participants who meet following criteria at any time during the entire study period (including the off-drug follow up time period) will be summarized by treatment group:

- treatment-emergent ECG abnormalities as listed in Table GPIA.6.10
- QT greater than 500 msec
- QTcF greater than 500 msec, and
- treatment-emergent increase from the maximum baseline in QTcF interval of greater than 30 msec, 60 msec, or 75 msec. Maximum baseline will be the maximum nonmissing observation in the baseline period. The maximum value during the treatment period will be analyzed. Scheduled and unscheduled measurements will be included.

 Table GPIA.6.10.
 Selected Categorical Limits for ECG Data

	Low		High		
Parameter	Males	Females	Males	Females	
Heart Rate	<50 and	<50 and	>100 and	>100 and	
(bpm)	decrease ≥15	decrease ≥15	increase $\geq 15$	increase ≥15	
PR Interval	<120	<120	>220	>220	
(msec)	<120	<120	≥220	≥220	
QRS Interval	<60	<60	>120	>120	
(msec)	<00	<00	≥120	≥120	
QTcF	<330	<340	>450	>470	
(msec)	~330	~340	~430	~4/0	

Abbreviations: bpm = beats per minute; ECG = electrocardiogram; QTcF = Fredericia's corrected QT interval.

## 6.13.6. Clinical Laboratory Evaluation

Limits from the performing lab will be used to define low (L) and high (H). Descriptive summaries by treatment and by nominal visit will be provided for the baseline and postbaseline values as well as the change from baseline values. The associated descriptive will be presented in System International (SI) units and in conventional (CN) units.

Observed and change from baseline values for each visit may be displayed in plots for participants who have both a baseline and at least 1 postbaseline planned measurement. Baseline will be the last nonmissing observation prior to taking first study drug. Unplanned measurements will be excluded from plots.

A shift table will be provided including unplanned measurements. The shift table will include the number and percentage of participants within each baseline category (low, normal, high, or missing) versus each postbaseline category (low, normal, high, or missing) by treatment. The proportion of participants shifted will be compared between treatments using Fisher's exact test.

For qualitative laboratory analytes, the number and percentage of participants with normal and abnormal values will be summarized by treatment.

A listing of abnormal findings will be created for laboratory analyte measurements, including qualitative measures. The listing will include participant identification, treatment group, laboratory collection date, study day, analyte name, and analyte finding.

The MMRM model or ANCOVA (if MMRM model is not applicable) will be used for the analysis during the treatment period for the continuous measurements for selected lab tests.

## 6.14. Health Outcomes

The patient-reported outcome questionnaires will be analyzed using the mITT population on the EAS, unless specified otherwise.

Item-level missingness is dealt with as per the instrument developers' instruction.

Additional psychometric analyses will be performed by Global Patient Outcomes Real World Evidence at Lilly and documented in a separate analysis plan.

## 6.14.1. Patient Global Impression of Status for Physical Activity

The counts and percents of participants for Patient Global Impression of Status for Physical Activity (PGIS) response categories at each time point will be summarized by nominal visit and by treatment. For time points >52 weeks, only the participants with prediabetes at randomization will be included so that the denominator for percents will be participants with prediabetes at randomization only. A shift table from baseline to postbaseline of 5 PGIS response categories will be created at each postbaseline visit.

## 6.14.2. Short-Form-36 Health Survey Version 2, Acute Form

Per copyright owner, the QualityMetric Health Outcomes™ Scoring (PRO\_CoRe V2.0) Software will be used to derive the following domain and component scores:

- Mental Component Score (MCS)
- Physical Component Score (PCS)
- Physical Functioning domain (PF)
- Role-Physical domain (RP)
- Bodily Pain domain (BP)
- General Health domain (GH)
- Vitality domain (VT)
- Social Functioning domain (SF)
- Role-Emotional domain (RE), and
- Mental Health domain (MH).

The following analyses for the actual value and change from baseline value for each domain and component score will be conducted:

- descriptive summaries by treatment group, and
- analysis described in Table GPIA.6.4.

If data allowed, analysis for SF-36 physical function domain score analysis described in Table GPIA.6.4 and in Table GPIA.6.4 will be conducted to evaluate the treatment effect in participants who have impaired physical function at baseline, which is defined as PGI-S response at baseline of "moderately limited", "very much limited," or "extremely limited". The empirical cumulative distribution function (eCDF) curves of the change from baseline to Week-52 in SF-36 physical function domain score will be provided by treatment group.

# 6.14.3. Impact of Weight on Quality of Life-Lite Clinical Trials

The following parameters will be included from IWQOL-Lite-CT:

- IWQOL Lite CT total score (all items: items 1 through 20)
- Physical Function composite score (5 items: items 1 through 3, 16, 17)
- Physical composite score (7 items: item 1 through 5, 16, 17), and
- Psychosocial composite score (13 items: item 6 through 15, 18, 19, 20).

IWQOL-Lite-CT total and composite scores range from 0 to 100, with higher scores reflecting better levels of functioning.

IWQOL-Lite-CT scores are computed according to the IWQOL-Lite scoring rules (Kolotkin et al. 2002) as following:

- Each composite raw score will be calculated if a minimum of 50% of the items for that composite has a non-missing value; the total score will be calculated if a minimum of 75% of all 20 items has a non-missing value.
  - physical composite score: 4 of 7 items
  - physical function composite score: 3 of 5 items
  - psychosocial composite score: 7 of 13 items
  - IWQOL Lite CT total score: 15 of 20 items
- If the minimum required number of items are answered for a composite then:
  - Calculate the average of the valid non-missing responses corresponding to the items in the total or each composite (1 = "never" or "not at all true" and 5 = "always" or "completely true").
  - The composite score is then calculated by transforming the raw composite score to the 0 (worst)-to-100 (best) metric using the following formula for every participant at each time point:

 $100 (S_{max} - C_{avg})/(S_{max} - S_{min})$ 

- $C_{avg}$  is the raw average score of all nonmissing item responses in the composite; this average must be a number between 1 and 5, inclusive
- $S_{max}$  is the maximum possible raw score value (that is, 5)
- $S_{min}$  is the minimum possible raw score value (that is, 1)
- Inserting the maximum and minimum possible score values, the formula is reduced to  $100 (5 C_{avg})/4$ .

For total and each composite score, the actual value and change from baseline value following analyses will be conducted:

- descriptive summaries by treatment group and
- ANCOVA analysis described in in Table GPIA.6.4

## 6.14.4. EQ-5D-5L

For the utility score and the Visual Analog Scale (VAS) scores, following analyses of the actual value and change from baseline value will conducted:

- descriptive summaries by treatment group and
- analysis of covariance described in Table GPIA.6.4.

## 6.15. Subgroup Analyses

Efficacy subgroup analyses will be guided by the efficacy estimand in EAS.

# 6.15.1. Subgroup Analysis of Body Weight Change

Subgroup analyses by the following baseline characteristics will be provided:

- age group (<65,  $\geq 65$  years)
- sex
- body mass index group (<28, ≥28 kg/m^2),
- body mass index group2 (<30,  $\geq 30$  and <35,  $\geq 35$  kg/m2), and
- presence of comorbidities at randomization (Y vs N).

The outcome measures for the subgroup analyses will include:

- percent change in body weight from randomization at 52 weeks and
- percentage of participants achieving at least 5% body weight reduction at 52 weeks.

For the percentage change in body weight from randomization at 52 weeks, for each subgroup analyses aforementioned, the following 2 models will be conducted:

- Conduct MMRM model on the subgroup only with terms of treatment group, visit, treatment-by-visit-interaction, sex, and presence of comorbidities at randomization as fixed effects, and baseline body weight as a covariate. Variance-covariance structure for within-patient errors will be same as Section 6.12.1.1
- Full MMRM model: treatment group, visit, subgroup, treatment-by-visit-interaction, treatment-by-subgroup-interaction, subgroup-by-visit-interaction, treatment-visit-subgroup-interaction, sex, and presence of comorbidities at randomization as fixed effects, and baseline body weight as a covariate. Variance-covariance structure for within-patient errors will be same as Section 6.12.1.1.

For the percentage of participants achieving at least 5% body weight reduction at 52 weeks, for each subgroup analyses aforementioned, the following 2 models will be conducted:

- Conduct logistic regression model on the subgroup only with terms of treatment group, sex, and presence of comorbidities at randomization as fixed effects, and baseline body weight as a covariate. Missing body weight measurement at 52 weeks will be imputed by the predicted value from MMRM model on the subgroup aforementioned, then the continuous measurements will be dichotomized into status of achieving at least 5% body weight reduction (Yes or No).
- Conduct logistic regression model with terms of treatment group, subgroup, treatmentby-subgroup-interaction, sex, and presence of comorbidities at randomization as fixed effects, and baseline body weight as a covariate. Missing body weight measurement at 52 weeks will be imputed by the predicted value from full MMRM model aforementioned, then the continuous measurements will be dichotomized into status of achieving at least 5% body weight reduction (Yes or No).

# 7. Unblinding Plan

Details of the blinding and unblinding will be provided in Blinding and Unblinding Plan document for Study GPIA.

# 8. COVID-19 Pandemic Impact

This section lists additional statistical analyses that may be performed at the primary database lock and final database lock to assess the impact of COVID-19 pandemic if the data warrants.

# 8.1. General Consideration

Percentage and count of randomized participants who followed the COVID-19 mitigation plan may be summarized by treatment group. This includes, but not limited to, participants rescreened, procedures conducted via remote visit or mobile home health visit, visits occurred using the extended visit windows, alternative way of investigator product shipment/dispensing, use of a local lab, etc. A listing of randomized participants who followed the COVID-19 mitigation plan may be provided. Similar analyses may be provided by country and by treatment group.

Percentage and count of randomized participants whose study visits were impacted by COVID-19 pandemic may also be summarized. A listing may be provided.

# 8.2. Exposure

A listing of randomized participants who had study drug temporary interruption due to COVID-19 pandemic may be provided.

# 8.3. Protocol Deviation

Percentage and count of randomized participants having important protocol deviation related to COVID-19 pandemic will be summarized by treatment.

Percentage and count of randomized participants with protocol deviation related to COVID-19 pandemic may also be summarized by treatment.

A listing of all randomized participants who had important protocol deviation due to COVID-19 pandemic may be provided.

# 8.4. Patient Disposition

A summary table for all randomized participants that discontinue study or study treatment due to COVID-19 pandemic will be provided by treatment.

A listing of randomized participants who discontinued the study or study treatment due to COVID-19 infection will be provided.

# 8.5. Adverse Events

A listing of randomized participants who had COVID-19 infection, including death due to COVID-19, during the post-randomization period will be provided.

# 8.6. Major Depressive Disorder/Suicidal Ideation

The counts and percentages of participants with TEAEs for major depression may be summarized by treatment group using MedDRA PT nested within SMQ by COVID-19 subgroup (that is, participants without impact versus with impact) for SS group.

A participant is defined as impacted by COVID-19 if either one of the following is satisfied:

• no COVID-19 illness, but impacted by quarantine and travel restrictions, clinics closing, visits being canceled, delay or nondelivery of the investigational product, virtual visits, etc.

OR

• with COVID-19 illness.

The suicidal ideation and behavior solicited through C-SSRS may be summarized by treatment group by COVID-19 subgroup (ie, participants without impact vs with impact) for SS group.

## 8.7. Missing Data Due to COVID-19

For the primary endpoints and key secondary endpoints, missing data due to COVID-19 will be handled as described in Section 6.12.1.3. In addition, a summary table for participants whose primary or key secondary measurements were impacted by COVID-19 (including missing, collected using alternative options) may be provided. A listing of participants whose primary or key secondary measurements were impacted by COVID-19 (including missing, collected using alternative options) may be provided. A listing of participants whose primary or key secondary measurements were impacted by COVID-19 (including missing, collected using alternative options) may be provided.

# Appendix 1. Searching Criteria for Special Safety Topics

### **Abuse Liability**

To identify AE terms suggestive of potential abuse liability, narrow terms from SMQ of Drug abuse and dependence (20000101) will be used.

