10.3. Statistical Analyses

10.3.1. General Statistical Considerations

Statistical analysis of this study will be the responsibility of Lilly or its designee. Any change to the data analysis methods described in the protocol will require an amendment ONLY if it changes a principal feature of the protocol. Any other change to the data analysis methods described in the protocol, and the justification for making the change, will be described in the SAP or the clinical study report. Additional exploratory data analyses may be conducted as deemed appropriate.

Unless otherwise noted, all tests of treatment effects will be conducted at a 2-sided alpha level of 0.05, and the confidence interval will be calculated at 95%, 2-sided. In statistical summaries and analyses, data will be analyzed as randomized.

Unless specified otherwise, efficacy and safety will be assessed using the modified intention-to-treat (mITT) population, which consists of all randomized participants who are exposed to at least 1 dose of study drug. Baseline is defined as the last non-missing data collected at randomization (prior to first dosing of study drug). Unless specified otherwise, safety assessments will compare safety of tirzepatide doses with placebo irrespective of adherence to study drug. Thus, safety analysis will be conducted using safety analysis set (SS).

Summary statistics for continuous measures will include sample size, mean, SD, median, minimum, and maximum. The analysis model to make comparisons among treatment groups relative to continuous measurements assessed over time will be a mixed model for repeated measures (MMRM), with terms of treatment, visit, and treatment-by-visit interaction, stratification factors, and baseline measurement as a covariate. An unstructured covariance structure will model relationship of within-patient errors.

Kaplan-Meier method will be used for estimation of cumulative event-free survival rates over time, and cox proportional hazards regression analysis will be used to compare hazard rates among treatments.

Summary statistics for categorical measures (including categorized continuous measures) will include sample size, frequency, and percentages. Logistic regression will be used to examine the treatment difference in binary efficacy outcomes if there is a need to adjust for covariates. Otherwise, Fisher's exact test will be used to examine the treatment difference in categorical outcomes.

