10.3.4.4.2. Events Related to Potential Abuse Liability

Two clusters of preferred terms for AEs suggestive of abuse liability will be analyzed. The first cluster includes Standardized MedDRA Queries (SMQ) of Drug abuse and dependence [20000101]. The second cluster is a Lilly Search Cluster "additional abuse potential" terms, which are additional terms suggestive of abuse liability that are not included in the SMQ Drug abuse and dependence [20000101].

Summaries and analyses for incidence of potential abuse liability terms will be provided by treatment. The details will be provided in SAP.

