# 6.13.1. Analysis of Adverse Events

## 6.13.1.1. Treatment Emergent Adverse Events

A treatment-emergent adverse event (TEAE) is defined as an event that first occurred or worsened in severity after baseline. The MedDRA Lowest Level Term (LLT) will be used in the treatmentemergent derivation. The maximum severity for each LLT during the baseline period including ongoing medical history will be used as baseline severity. For events with a missing severity during the baseline period, it will be treated as "mild" in severity for determining treatment-emergence. Events with a missing severity during the postbaseline period will be treated as "severe" and treatment-emergence will be determined by comparing to baseline severity.

For events occurring on the day of first taking study medication, the case report form (CRF)collected information (for example, treatment emergent flag, start time of study treatment and event) will be used to determine whether the event was pre- versus post-treatment if available. If the relevant information is not available, then the events will be counted as post-treatment.

The counts and percentages of participants with TEAEs will be summarized by treatment using MedDRA Preferred Term (PT) nested within System Organ Class (SOC). Statistical comparisons will be applied at both the SOC and PT levels. Events will be ordered by decreasing frequency within SOC. The SOC will be in alphabetical order. For events that are sex-specific, the denominator and computation of the percentage will include only participants from the given sex.

An overview of the number and percentage of participants who experienced a TEAE, serious adverse event (SAE), death, discontinued from study treatment or study due to an AE, relationship to study drug will be summarized by treatment.

The counts and percentages of patients with TEAEs by maximum severity will be summarized by treatment using MedDRA PT. For each participant and TEAE, the maximum severity for the MedDRA PT is the maximum postbaseline severity observed from all associated LLTs mapping to the MedDRA PT. The maximum severity will be determined based on the nonmissing severities. If all severities are missing for the defined postbaseline period of interest, it will show as missing in the table.

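### The SAP's abuse-liability search covers one of the two term clusters the protocol commits to, and gives no reason for leaving out the other

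*SAP*

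**What the plan says.** Protocol 10.3.4.4.2 (Events Related to Potential Abuse Liability) opens with a commitment: "Two clusters of preferred terms for AEs suggestive of abuse liability will be analyzed". The first cluster is the standardised MedDRA query Drug abuse and dependence, code 20000101, with no restriction of scope stated. Of the other, the protocol says "The second cluster is a Lilly Search Cluster" and describes its content as "additional terms suggestive of abuse liability that are not included in the SMQ Drug abuse and dependence [20000101". The section leaves the details of the analysis to the SAP.

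SAP 6.13.3.16 (Abuse Liability) plans counts and percentages of participants with treatment-emergent potential abuse-liability events by treatment group. For the definition of those events it says only that "Detailed searching criteria can be found in Appendix 1". The Abuse Liability entry in Appendix 1 is a single sentence, under which "narrow terms from SMQ of Drug abuse and dependence (20000101) will be used". It names no second cluster and attaches no term list.

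Protocol 10.3.1 sets the rule for departures. A change to the analysis methods that does not alter a principal feature of the protocol needs no amendment, but the change and "the justification for making the change, will be described in the SAP or the clinical study report".

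**The concern.** The protocol promises two searches and the SAP carries out one. The one it leaves out cannot be recovered from the one it keeps, because the protocol defines the second cluster by what the query does not contain.

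What is at stake is the completeness of one prespecified safety summary. The purpose of a term cluster is to count participants with any of a set of related terms, so that scattered reports under different preferred terms can be seen together. If the cluster is not searched, the abuse-liability table will look like the assessment the protocol described while covering only part of it. A reader of the table alone could not tell.

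**Working it through.** No arithmetic applies. The question is which terms each document searches, so the check sets the two side by side.

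| Item | Protocol 10.3.4.4.2 | SAP 6.13.3.16 with Appendix 1 |
|---|---|---|
| Number of clusters | 2 | 1 |
| Query 20000101 | Included, scope not stated | Included, narrow terms only |
| Sponsor cluster of additional abuse-potential terms | Included | Not mentioned |
| Reason given for a difference | Not applicable | None |

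1. **Is the second cluster elsewhere in the SAP?** No. Section 6.13.3.16 points only to Appendix 1, the Appendix 1 entry names only the query, and no other section of the SAP refers to the sponsor cluster.

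2. **Could the query pick up second-cluster terms anyway?** No. The protocol defines those terms as not included in query 20000101. The overlap is therefore zero by definition, and restricting the query to narrow terms cannot create any. Every second-cluster event falls outside the SAP's search.

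3. **Are the events lost from the study's reporting?** No. SAP 6.13.1.1 states: "The counts and percentages of participants with TEAEs will be summarized by treatment using" preferred term nested within system organ class, with comparisons at both levels. That section also tabulates events by maximum severity, and SAP 6.13.1.4 lists all serious events. What those tables do not provide is the number of participants with at least one abuse-related term. Adding up preferred-term rows does not give that number either, because one participant can contribute to several rows.

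4. **Does another SAP provision cover the gap?** SAP 6.2 allows analyses described in the SAP to be skipped when the data do not warrant them, and allows further analyses to be added. The first provision does not apply, because the second cluster is not described in the SAP. The second is a permission and does not restore a commitment made in the protocol.

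5. **Has the protocol's rule on changes been met?** Not so far. Protocol 10.3.1 asks for the change and its justification in the SAP or the clinical study report, and the SAP gives neither. The report remains open as a route, but a reason given there would come after the data are known.

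6. **What of the narrow-term limit?** The protocol states no scope, and the SAP sets scope topic by topic in Appendix 1: narrow for gallbladder disease, broad and narrow for most of the hepatic queries, mixed for arrhythmias. The limit therefore reads as a choice the SAP has made. It has one practical consequence. If the query also has broad-scope terms (the documents do not say), those terms would fall outside both searches even after the second cluster is restored, because the second cluster excludes everything in the query. The intended scope therefore needs to be confirmed as part of the same correction.

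**The case against.** The strongest reply is that little turns on this. Abuse liability is not among the study's objectives or endpoints, nor in the protocol's list of adverse events of special interest (10.3.4.3). It stands under other adverse event assessments. Second-cluster events are still collected, coded, tabulated by arm and compared in the general tables. The protocol hands the details to the SAP, the SAP is open about the search it uses, and protocol 10.3.1 allows a non-principal change of method to be explained as late as the clinical study report.

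Most of this stands, and it is why the point is a minor one. It does not remove the inconsistency. Leaving the details to the SAP covers how the two clusters are analysed, not whether the second is analysed at all. The permission to change methods comes with a duty to describe and justify the change, which the SAP has not done.

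Three stronger readings are tempting, and the documents do not support them:

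- **That these events would never be counted.** They would be counted, as individual preferred terms under SAP 6.13.1.1. Only their grouping under abuse liability is lost.
- **That the summary would be biased towards showing no signal.** The same search applies to every arm. A narrower search lowers ascertainment, but whether the tirzepatide-placebo contrast shifts, and in which direction, depends on which terms the sponsor cluster holds and how they fall across arms. The documents list no terms.
- **That the narrow-term limit contradicts the protocol.** The protocol is silent on scope and defers details to the SAP. The limit needs confirming, but it is not a conflict.

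**Conclusion.** The inconsistency is real and of low severity. The protocol commits to two abuse-liability clusters, the SAP searches one, and no reason is given. As written, every second-cluster event is excluded from the summary in SAP 6.13.3.16, so that summary under-ascertains what the protocol meant it to capture. This rests only on the protocol's own definition of the second cluster and on the SAP's silence about it.

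The size can be stated no further than that: one of two clusters, and all of its terms. A reader might want a number of missed participants, but the documents give neither a rate for such events nor the cluster's contents, so any figure would be guesswork. No primary or key secondary result depends on the point.

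Whether the omission was deliberate cannot be settled from the documents. Appendix 1 also carries search criteria for amputation and peripheral revascularisation, a topic with no analysis section in SAP 6.13.3. This suggests that the appendix was not fully matched to this study, but that is an inference and the finding does not depend on it.

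**What to change.** In SAP Appendix 1, under Abuse Liability, add the sponsor's second cluster with its list of preferred terms. In SAP 6.13.3.16, summarise by treatment the participants with an event in each cluster and in the union of the two, counting a participant with terms in both once in the union. In the same entry, state whether query 20000101 is meant to be narrow scope only.

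If leaving out the second cluster was intended, keep the single search and record the change with its reason, as protocol 10.3.1 requires. The SAP is the better place for this, because the decision then remains prespecified.

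The cost is small. The protocol names the cluster as the sponsor's own, so the work is a term list and one or two table rows, or a sentence of justification. No new data are collected, and no other analysis changes.
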